1.1.14. **Health Behaviors:** Physical activity and medication adherence will be the target behavioral outcome measures. We will use the well-validated Actigraph GT3X+ accelerometer,⁷⁴ at baseline, Week 9, and Week 18, for 7 days of wear; minimum acceptable use is 4+ days with 10+ hours of recorded data as in prior guidelines⁷⁵⁻⁷⁷ to measure minutes/day of light activity (100-1951 counts/min⁷⁸) as our primary activity measure, along with sedentary leisure time (SLT),^{74, 79} given their links to health outcomes. Medication (specifically immunosuppressant, tacrolimus or sirolimus) adherence will be measured via the widely used electronic pill monitoring system, MEMS Caps,⁸⁰ to electronically monitor immunosuppressant adherence over the duration of the study. From the EHR and confirmed by patients, we will determine immunosuppressant medication and dosing, and we will calculate changes in adherence over time (% of medication correctly taken, by week and month), based on MEMS data. Additionally, we will assess self-reported adherence to Tacrolimus (an immunosuppressant medication which all allogeneic HSCT patients must take) with the Medication Adherence Scale-5 (MARS-5).^{81, 82} (Appendix T)

9.5 Data from the Electronic Health Record:

Study staff will collect clinical, disease, and transplant characteristics at baseline including: ECOG Performance Status at the time of HSCT, clinical comorbidities as measured by the HCT-Comorbidity Index,⁸³ underlying diagnosis, date of diagnosis, disease status at the time of HSCT, disease risk based on the Disease Risk Index,⁸⁴ conditioning regimen, donor type, donor source, date of HSCT, and hospital length-of-stay. We will also collect data on the incidence and severity of acute and chronic GVHD and the incidence of relapse at one year post-HSCT as these outcomes are associated with QOL.

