any participants refuse or are unable to complete the questionnaires on the computer, they will be permitted to use hard-copy paper versions of the questionnaires. Participants will also be provided the option to complete questionnaires over the phone. The CRC will contact participants (in person or via telephone) daily for two days to remind them to complete and return the surveys. If study participants fail to complete the surveys within seven days of the expected time point, we will report the data as missing and document the reason for incompleteness. Table 4 details the schedule for administering the self-report measures. At enrollment all participants will be mailed the *Actigraph GT3X+* (together with instructions (Appendix V) on how to use the *Actigraph*) for 7 days of wear; minimum acceptable use is 4+ days with 10+ hours of recorded data around day 85-95 post-transplant and prior to the intervention initiation around day 100 post-transplant. After baseline physical activity data collection, participants will mail back the *Actigraph* in prepaid envelopes we will provide. In addition to the *Actigraph*, participants will also be mailed the MEMS Cap (together with the instructions (Appendix W) on how to use the MEMS Cap) for medication (immunosuppressant) adherence assessment over the entire duration of the intervention starting at the time of baseline surveys around day 85-95 post-transplant. All participants will complete baseline assessments approximately 85-95 day post-transplant. All participants will then complete follow-up assessments at Week-9 (with a 1 week window) and at Week-18 (+/- 1 week window) of intervention initiation.

Table 4: Administration of Self-Report Measures

Participant	Baseline	Week-9 (+ 1 week window)	Week-18 (+/- 1 week window)
Patient Measures:			
Demographics	X		
FACT-BMT	X	X	X
PROMIS-Fatigue 8a	X	X	X
PROMIS-PF-20	X	X	X
HADS	X	X	X
PCL (PTSD)	X	X	X
LOT-R	X	X	X
PANAS	X	X	X
GQ-6	X	X	X
SWLS	X	X	X
Flourishing Scale	X	X	X
Brief Cope	X	X	X
MARS-5	X	X	X
SSEQ	X	X	X
Accelerometer	X	X	
MEMS-Cap		Longitudinal from baseline through week 9	

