Follow-up assessments: During Week 8 of the intervention, all participants (those in the intervention group and the usual care group) will be mailed (or given in-person during a routine follow-up clinic visit) an accelerometer to wear for 7 days in order to assess physical activity at follow-up. Then, at Week 9, participants will return the accelerometer and MEMS Cap, and will repeat self-assessment questionnaires obtained at the beginning of the study either in-person during a routine follow-up clinic visit, over the phone, or via a REDCap survey link e-mailed to them, depending on participant's preference. Furthermore, participants in the intervention group will be asked to provide feedback about the program via a recorded exit interview over the phone.

Positive Psychology Program Content: All phone sessions will include (a) a review of the ease and utility of the week's PP exercise, (b) a discussion of the rationale of the next week's PP exercise through a guided review of the PP manual, and (c) assignment of the next week's PP exercise. During the calls, the interventionist and participant will also review the next section of the treatment manual and prepare for the upcoming week's exercise.

9.8 *Procedures performed to lesson the probability or magnitude of risks*

We will ensure that contact with participants is confidential by using only the phone numbers and other contact information that are specifically allowed by the participants. We will not leave study-related messages for participants unless expressly allowed by participants. Upon enrollment, we will ask all participants for the preferred times for calls and if it is acceptable to leave voice messages on their phones. We will adhere to any and all patient requests regarding contact.

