Specific Aim 3 (Effects on Health Behaviors): To examine the impact of the PATH intervention on behavioral outcomes (e.g., medication adherence, physical activity) compared to those in the usual care condition: We will initially compare physical activity (# of steps/day) at 9- and 18-weeks between the intervention and control groups using a Wilcoxon rank sum test, given that the distribution of the number of steps will likely be skewed. We will also use random effects regression models with a random intercept for each participant to compare between-group differences in change over time in physical activity and medication adherence. All statistical tests will be two tailed, with $p < 0.05$ considered significant.

Missing Data: We will also use the intention-to-treat principle with all randomized participants and conducting sensitivity analyses to explore various assumptions about missing data. If source of the missing data appear to be missing at random, the linear mixed effects models described above provide an unbiased estimate of the regression coefficients. However, if we find that participants do not complete the study because of disease worsening, suggesting missing data are not random, we will employ pattern mixture modeling or joint modeling approaches⁹⁰ to handle incomplete data, and perform sensitivity analysis⁹¹ to assess the impact of missing data. In addition to the intention-to-treat analysis, we will also estimate the group differences in the completers to estimate the per protocol group difference.

10.2. Sample Size Calculation & Power Analysis:

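### Week-18 accelerometry appears in Section 9.4 and in the Aim 3 analysis but not in Table 4, and Aim 3 does not say which activity metric its longitudinal model uses

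*Combined protocol and SAP*

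**What the plan says.** **Timing.** Section 9.4 (Health Behaviors) has the Actigraph worn "at baseline, Week 9, and Week 18, for 7 days of wear". Section 10.1, Specific Aim 3, follows that schedule: "We will initially compare physical activity (# of steps/day) at 9- and 18-weeks between the intervention and control groups", by a Wilcoxon rank sum test. Table 4 in Section 9.6 gives the accelerometer two marks, at baseline and Week 9, and none at Week 18. Section 9.7 describes one follow-up issue of the device: "During Week 8 of the intervention, all participants (those in the intervention group and the usual care group) will be mailed" an accelerometer, or given one in clinic. It continues: "Then, at Week 9, participants will return the accelerometer and MEMS Cap". Section 9.1 likewise describes one follow-up wear, shortly before the end of the nine-week intervention.

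**Metric.** Section 9.4 takes minutes per day of light activity "as our primary activity measure, along with sedentary leisure time (SLT"). Section 10.1 names steps per day for the Wilcoxon test and justifies the test "given that the distribution of the number of steps will likely be skewed". It then adds random-intercept models "to compare between-group differences in change over time in physical activity and medication adherence", without saying which activity variable is modelled or at which time points.

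**The concern.** The analysis section plans a comparison at a time point for which the schedule of assessments collects no activity data. A coordinator working from Table 4 would not issue a device for Week 18, and the data could not be recovered once the window had passed. The loss would affect every participant by design, so it is not the participant-level missingness that the missing-data paragraph of Section 10.1 addresses. Durability of any effect on measured activity could then not be assessed.

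The metric problem is separate and would remain even if the timing were settled. Section 9.4 ranks one accelerometer variable as primary, and the only variable named in the analysis section is a different one that Section 9.4 does not list. With three candidate variables (light activity, sedentary time, steps) and two methods, the choice of which result to report as the effect on activity is left open until after the data are seen.

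**Working it through.** The plan states no figure for this point, so the check sets the sections side by side and counts.

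**1. Week-18 accelerometer wear, by section**

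| Place | Week-18 wear? |
|---|---|
| Section 9.4, Health Behaviors | Yes, listed |
| Section 10.1, Aim 3 | Yes, assumed by the 18-week comparison |
| Section 9.6, Table 4 | No mark |
| Section 9.1 | One follow-up wear, before the Week-9 survey; none described for Week 18 |
| Section 9.7 | Sent in Week 8, returned at Week 9; no later issue described |
| Section 13.0 | Device mailed back after 7 days; fits any number of wears |

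**2. Is the blank in Table 4 a general gap in the Week-18 column?** No. All 13 repeated questionnaires (FACT-BMT, PROMIS-Fatigue, PROMIS-PF-20, HADS, PCL, LOT-R, PANAS, GQ-6, SWLS, Flourishing Scale, Brief Cope, MARS-5, SSEQ) carry three marks; the accelerometer row carries two. The MEMS row next to it gives its own period as "Longitudinal from baseline through week 9".

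**3. Size of the timing discrepancy**
- Wear periods under Section 9.4: 3 × 70 = 210.
- Wear periods under Table 4: 2 × 70 = 140.
- Difference: 210 − 140 = 70, which is the whole Week-18 wear.
- Wilcoxon comparisons planned: 2 (Weeks 9 and 18). Possible under Table 4: 1.

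**4. Consequence for the longitudinal model.** Aim 2 specifies a random-intercept model with time as baseline, Week 9 and Week 18. If that structure carries over to Aim 3, which is the natural reading although it is not stated, the Week-18 time-by-group term for activity has no data under Table 4.

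**5. Metrics**
- Named in Section 9.4: light-activity minutes per day (primary) and sedentary leisure time.
- Named in Section 10.1: steps per day.
- Section 9.4 metrics that Section 10.1 names: 0 of 2.

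**6. Power is not the issue.** Section 10.2 gives a detectable effect of d = 0.74 at 80% power with 30 completers per group. At two-sided alpha 0.05, a two-sample t-test gives power of 80.5% at d = 0.74 and a detectable d of 0.736 at 80% power, so the figure reproduces. It has no bearing on either discrepancy.

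**The case against.** **The procedural sections are weak corroboration.** A reader might infer that Sections 9.1 and 9.7 show that no Week-18 wear is intended. They do not go that far. Neither section describes the Week-18 visit; each mentions 18 weeks only in connection with payment. Yet Week-18 questionnaires are clearly planned in Table 4 and in the text above it, so silence about a Week-18 device is to be expected under either intention. Section 9.1 also has the devices returned when the study ends, which could suggest a later wear, although it describes none. The positive conflict is therefore Sections 9.4 and 10.1 against the blank cell in Table 4. That cell was read by machine, but the other rows kept their marks and the Demographics row kept its blanks, so the blank is probably genuine. The point stands as a contradiction to be reconciled, with no inference about which version the sponsor meant.

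**The primary measure may have an analysis.** A reader might infer that light activity has no planned analysis at all. That is too strong. Aim 3 models change in physical activity, and Section 9.4 defines the primary measure of physical activity; read together, the model can cover light-activity minutes. What stands is that Section 10.1 does not say so, and the only activity variable it does name is steps.

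**These are secondary endpoints in a pilot.** This is correct and limits the weight of the point. It does not excuse a scheduled comparison without data, or an outcome left undefined when the fix is cheap.

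**Conclusion.** Both parts hold. On timing, the plan contradicts itself: Sections 9.4 and 10.1 include Week-18 accelerometry and Table 4 does not. If Table 4 is followed, Week-18 activity is available for 0 of 70 participants and one of two Wilcoxon comparisons is empty. If Section 9.4 is followed, the comparison can be run, but the documents give no basis for saying how many participants would have usable Week-18 wear. On metric, Section 10.1 names neither variable declared in Section 9.4 and leaves the outcome of the random-intercept model unstated.

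The conclusion rests on taking the blank Table 4 cell as genuine. A reader might extend it to the trial's main conclusions; the documents do not support that. The primary endpoint is feasibility and acceptability, the Week-9 activity comparison can be run under either reading, and Week-18 questionnaires, including MARS-5, are scheduled. The effect is confined to secondary behavioral endpoints in a trial that Section 10.2 says is not designed to detect group differences on them.

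**What to change.** **Timing: choose one.**
- Keep Week 18: add the accelerometer to the Week-18 column of Table 4, and describe its dispatch, 7-day wear and return in Sections 9.1 and 9.7. Cost: up to 70 more mailings and 70 more prepaid returns, plus 7 further days of wear for each participant.
- Drop Week 18: delete it from the accelerometer sentence in Section 9.4 and from the Aim 3 activity comparison. Cost: wording only.

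**Metric.** In Section 10.1, name light-activity minutes per day, the sponsor's own declared primary measure, as the outcome of the random-intercept model, and list the time points actually collected. State which analyses apply to sedentary leisure time and to steps per day. The ranking of those two is for the sponsor, since Section 9.4 does not place sedentary time below light activity. Cost: wording only.

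Either route means amending the document, and the timing should be settled before participants reach Week 18.

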9.7 Overview of Research Procedures

Initial/Enrollment phone call: During this initial approach at a routine outpatient follow-up clinic or phone call, the study procedures will be explained to potential participants. Those who are interested will be screened for eligibility and, mailed or e-mailed a copy of the study information

PROTOCOL TITLE: Randomized Trial of a Positive Psychology Intervention for Patients with Hematologic Malignancies Undergoing Hematopoietic Stem Cell Transplantation

sheet. We will then call patients upon receipt of the information sheet approximately seven days from receipt of the information sheet for enrollment and written consent procedures during a routine clinic visit or verbal consent procedures over the phone. Consented participants will then be randomized to usual care or the intervention group. All participants will be mailed (or given in person at a routine follow-up visit) the electronic pill bottle (MEMS Caps), and the accelerometer (Actigraph GT3X+, small half-dollar sized device that clip on to a belt with no visible readout thus preventing independent subject access to data) to wear for 7 days prior to the intervention initiation in the control group. Participants in the intervention group will also be mailed the study intervention manual together with their accelerometer and electronic pill bottle. At the time of the baseline survey and prior to the start of the intervention, adequate accelerometer wear (at least 4 days with 10+ hours per day worn) will be confirmed. Participants in the intervention group will also be mailed the study intervention manual. Those who have not completed sufficient wear of the device will be asked to re-wear the device until there is sufficient baseline data available.

Baseline Assessments: Around the time of each participant's routine 85-95-day post-transplant routine clinic visit, participants will be asked to complete baseline assessment questionnaires either in person during a routine follow-up visit in clinic, over phone, or via a REDCap survey link that will be e-mailed to participants.

After completion of the baseline survey and a returned accelerometer with adequate data, the interventionist will review the mailed treatment manual with weekly PP exercises to those in the intervention group. Participants in the intervention group will be assigned the first exercise (gratitude for positive events) in preparation for their first phone session.

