We will compare between-group differences in change over time in all patient-reported outcome measures (i.e., psychological, functional, and QOL outcomes) at the 9 and 18-week time points using random effects regression models with a random intercept for each patient. Longitudinal analyses will include all time points. The model will include a categorical effect of time (baseline, week 9 and week 18), a group effect and a time by group interaction. The time by group interaction will estimate the difference in the change from baseline to each time point, and these regression coefficients will be the focus of the analysis.

Given that this pilot is not powered to detect statistically significant group differences, we will examine difference in the change with time and sample variance components on the secondary outcomes. Effect sizes (Cohen's d) will be calculated for changes in outcomes from baseline to 9 and 18 weeks, where 0.3 indicates a small effect, 0.5 a medium effect, and 0.8 a large effect.⁸⁸ Effect sizes will be used in a power analysis to estimate the necessary sample size to conduct a full-scale efficacy trial with power >80%. We will also verify the needed sample size based on ability to detect a clinically meaningful difference and references to existing literature.⁸⁹

Finally, we will explore (1) possible mediators of the intervention (e.g., coping strategies) by examining the bootstrapped confidence intervals of the indirect effects and (2) possible moderators (e.g., social support) of intervention effects by probing interactions between the moderator and group assignment that reach or approach significance ($p<0.15$) when predicting patient-reported outcomes.

PROTOCOL TITLE: Randomized Trial of a Positive Psychology Intervention for Patients with Hematologic Malignancies Undergoing Hematopoietic Stem Cell Transplantation

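### The first-listed activity test in Aim 3 has no baseline or GVHD term, and the change model beside it neither governs nor uses baseline efficiently

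*Combined protocol and SAP*

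**What the plan says.** Section 10.1, Specific Aim 3, plans two analyses of physical activity.

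- **First-listed:** "We will initially compare physical activity (# of steps/day) at 9- and 18-weeks", "between the intervention and control groups using a Wilcoxon rank sum test". The reason given is skew: "given that the distribution of the number of steps will likely be skewed". No baseline or GVHD term is mentioned.
- **Second:** random effects regression with a random intercept per participant, "to compare between-group differences in change over time in physical activity and medication adherence". Aim 3 does not write this model out. The model of the same kind under Aim 2 is specified: "The model will include a categorical effect of time (baseline, week 9 and week 18), a group effect and a time by group interaction". There, the interaction estimates the difference between arms in change from baseline.

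Both fall under one rule: "All statistical tests will be two tailed, with $p < 0.05$ considered significant". Neither is named as the governing analysis.

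On data, section 9.4 schedules the accelerometer "at baseline, Week 9, and Week 18, for 7 days of wear" and names minutes per day of light activity as the primary activity measure, whereas Aim 3 tests steps per day. Section 9.7 says that participants with too little baseline wear are "asked to re-wear the device until there is sufficient baseline data available". Section 5.1 makes baseline accelerometer data a condition of registration and accrual, with randomisation after registration. Sections 3.0 and 9.1 stratify randomisation by GVHD because recovery, quality of life and function differ by GVHD status.

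**The concern.** Baseline activity is likely to be among the better predictors of follow-up activity, and the protocol takes trouble to collect it before the intervention starts. Skew is a reason to use ranks or a transformation. It is not a reason to leave out baseline, because rank-based and transformed analyses can both carry covariates. The stratification factor was chosen because it predicts function, yet it is absent from the test too.

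Three things are at stake, all modest: precision in a comparison with about 30 participants per arm; a clear answer if the two analyses disagree at 0.05; and the quality of the effect estimate. Section 10.2 says the pilot is meant to give tentative effect sizes, and a rank-sum p-value supplies no baseline-adjusted estimate.

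**Working it through.** **Inputs from the documents.** 30 completers per arm and a detectable d of 0.74 at 80% power (section 10.2); 1:1 allocation (sections 3.0 and 9.1); two-sided 0.05 (section 10.1, Aim 3).

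**Assumed inputs.** The correlation r between baseline and follow-up activity is not given, so r = 0.3, 0.5 and 0.7 are shown. d = 0.5 is illustrative; section 10.1 calls it a medium effect.

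**Step 1: the plan's own figure.** For a two-sample t test with 30 per arm (noncentral t, 58 degrees of freedom), power at d = 0.74 is 80.5%, and d for exactly 80% power is 0.736. The stated 0.74 reproduces. It assumes no baseline adjustment.

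**Step 2: variance relative to follow-up alone.** Assume complete data and equal variances at each visit.

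- Change from baseline, which is what the Aim 2 form of the model estimates: 2(1 − r).
- Baseline as a covariate: 1 − r².
- Ratio of the second to the first: (1 + r)/2, which is below 1 for every r below 1.

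| r | Change, 2(1 − r) | Covariate, 1 − r² |
|---|---|---|
| 0.3 | 1.40 | 0.91 |
| 0.5 | 1.00 | 0.75 |
| 0.7 | 0.60 | 0.51 |

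The change model matches follow-up alone at r = 0.5, is worse below that and better above it.

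**Step 3: normal-theory power at d = 0.5.** Divide d by the square root of the variance factor and use the same noncentral t. For example, at r = 0.5 with baseline as a covariate, 0.5/√0.75 = 0.577, which gives 59%.

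| r | Follow-up only | Change | Covariate |
|---|---|---|---|
| 0.3 | 48% | 36% | 51% |
| 0.5 | 48% | 48% | 59% |
| 0.7 | 48% | 69% | 76% |

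On the plan's own scale, the detectable d of 0.74 becomes 0.74 × √(1 − r²) = 0.71, 0.64 and 0.53 with baseline as a covariate.

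**Step 4: check on skewed data.** The power figures in step 3 are for a t test, not the Wilcoxon test. A simulation used lognormal activity (assumed log SD 0.6), a shift of 0.74 SD on the log scale, 30 per arm and 3,000 runs per setting.

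| r | Wilcoxon, follow-up only | Rank ANCOVA | ANCOVA on logs | Change on logs |
|---|---|---|---|---|
| 0.3 | 78% | 81% | 84% | 66% |
| 0.5 | 79% | 88% | 90% | 81% |
| 0.7 | 78% | 96% | 98% | 95% |

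The simulated type I error was between 4.2% and 5.4% for all four. The pattern matches step 2: the gain from adjustment is small at r = 0.3 and large at r = 0.7.

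**Step 5: chance imbalance.** The standard error of a baseline difference is √(2/30) = 0.26 SD, so a difference above 0.3 SD in either direction arises in about 25% of trials. A follow-up-only test cannot allow for it in the one trial that is run.

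**The case against.** A reader who stops at the Wilcoxon sentence might infer that the plan discards the baseline accelerometer data. It does not: the next sentence adds a model of change over time in physical activity, which uses baseline if it follows the Aim 2 form. Nor does the text make the Wilcoxon test decisive. Its wording fits a simple first look before modelling.

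It would also be tempting to quote 48% against 59% to 76% as what adjustment adds to this plan. That compares adjustment with using no baseline at all. Against the planned change model, the gain at r = 0.7 is 76% − 69% = 7 points, and at r = 0.5 it is 59% − 48% = 11 points. Nor is 48% established as the Wilcoxon power for these data. With skewed outcomes, Wilcoxon power depends on the shape of the distribution and the form of the effect. In one simulation with lognormal data and a location shift of 0.5 raw SD, it was about 73%, against 52% for the t test.

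Nor is the unadjusted test biased; under randomisation it is valid. Finally, activity is a secondary endpoint (section 8.0) in a pilot that section 10.2 says is not designed to detect group differences definitively.

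All of this stands, and it limits the size of the point. It does not supply a governing analysis, a way to handle skew in the change model (the check on normality and transformation is described under Aim 2), or the precision that baseline as a covariate would give over both planned analyses.

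**Conclusion.** The point holds in limited form. The first-listed test leaves out both baseline activity and the randomisation stratum. The change model brings baseline in, but gains nothing over follow-up alone at r = 0.5 and loses below it. No rule says which result counts. Baseline as a covariate has lower variance than the change score at every r below 1, and lower than follow-up alone whenever r is not zero.

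The size depends on r, which the documents do not give. At r = 0.3 the variance saving over follow-up alone is only 9%; at r = 0.7 it is 49%. The change-model figures also assume that Aim 3 uses the Aim 2 specification, with complete data and equal variances. The gain from adding GVHD cannot be sized from the documents.

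The documents do not support saying that baseline is ignored throughout Aim 3 or that the comparison is biased. It is also too firm to say that every randomised participant will certainly have baseline accelerometer data. Section 5.1 requires them before registration, but section 21.0 ties registration to baseline questionnaires only, and section 9.7 mentions randomisation before it describes handing out the device.

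**What to change.** In section 10.1, Aim 3, name one governing activity analysis that tolerates skew and adjusts for baseline activity and GVHD stratum. Rank ANCOVA would do, as would ANCOVA or a longitudinal model of week 9 and week 18 on transformed activity with baseline as a covariate. Keep the Wilcoxon test as a descriptive check.

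Apply the analysis to the measure that section 9.4 names as primary, minutes per day of light activity, and reconcile this with steps per day in Aim 3. Also reconcile sections 5.1, 9.7 and 21.0 on whether adequate baseline accelerometer data are required before randomisation, since the adjusted analysis relies on them. A separate matter to settle in the same edit is that Table 4 in section 9.6 lists the accelerometer at baseline and week 9 only, while section 9.4 and Aim 3 also use week 18.

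The analysis change costs a sentence or two. The adjustment itself needs no new data and no more participants.
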